### 9.6.1 Permitted Concomitant Therapies

The Investigator may prescribe concomitant medications or treatments for pain (acetaminophen up to 2000 mg per 24 hr, ibuprofen up to 600 mg per 24 hr administered orally) or nausea (promethazine 25 mg oral or suppository) as deemed necessary for the comfort of the subject. For oral therapies, please withhold dosing for at least 2 hr before or 1 hr after administration of IMP.

### 9.6.2 Prohibited Concomitant Therapies

Subjects should be instructed not to take any medications, including over-the-counter products, without first discussing with the Investigator.

The following medications are CYP3A4 inhibitors and are expressly prohibited during the study:

Strong inhibitors of CYP3A4 include clarithromycin, telithromycin, nefazodone, itraconazole, ketoconazole, atazanavir, darunavir, indinavir, lopinavir, nelfinavir, ritonavir, saquinavir, tipranavir. Moderate inhibitors of CYP3A4 include amiodarone, erythromycin, fluconazole,

miconazole, diltiazem, verapamil, delavirdine, amprenavir, fosamprenavir, conivaptan. Cimetidine is an over-the-counter medication that is a weak CYP3A4 inhibitor.

Indivior or specified designee should be notified if a subject receives any of these medications during the study.

## 9.6.3 Lifestyle Restrictions

## 9.6.3.1 Fluid and Food Intake

Subjects are required to fast a minimum of 8 hours before blood sample collection at screening.

In accordance with the exclusion criteria, subjects will not be permitted to eat poppy seeds, grapefruit or Seville oranges or drink grapefruit juice or Seville orange juice within 7 days prior to study drug administration.

Restrictions for water and food intake related to study drug administration are discussed in Section 9.3.

## 9.6.3.2 Subject Activity Restrictions

While participating in the study, subjects will not be permitted to perform heavy exercise. Subjects are asked to refrain from heavy exercise starting 24 hours before IMP administration.

### 9.6.3.3 Caffeine, Alcohol and Tobacco Restrictions

Subjects will not be permitted to drink caffeine-containing beverages, eat caffeine-containing foods or use caffeine-containing products prior to check-in through the EOS visit.

In addition to 90 days prior to screening, subjects will refrain from smoking and from using ecigarettes and nicotine-containing products through the EOS visit.

Subjects will refrain from drinking alcohol from prior to check-in through the EOS visit.

## 9.7 Compliance

The PI or sub-Investigator may terminate a subject based on the subject's ability to comply with the protocol requirements.

Study drug will be administered by designated qualified study personnel at the clinical facility. The PI or sub-Investigator will be present during the administration of study drug. The time and duration, the dose delivered and any dosing observations will be recorded in source documentation. The PI, sub-Investigator or designated individual will maintain a log of all study drugs dispensed and returned. Drug supplies will be inventoried and accounted for throughout the study. The clinical site will have access to the Indivior Medical Monitor for any safety events that occur.

# 10 ADVERSE EVENTS

The Investigator or designee is responsible for identifying, documenting and reporting events that meet the definition of an AE.

An AE is any untoward medical occurrence in a subject associated with the use of an IMP regardless of the presence of a causal relationship to the IMP. An AE can be any unfavourable and unintended sign (including an abnormal laboratory finding) symptom or disease (new or exacerbated) temporally associated with an IMP, whether or not considered related to the IMP.

- Events meeting the definition of an AE include:
- New condition detected after IMP administration even though the AE may have been present prior to receiving IMP.
- Exacerbation of a pre-existing condition (including intensification of a condition and/or an increase in frequency).
- Any abnormal laboratory test results or other safety assessments felt to be clinically significant in the opinion of the Investigator (including those that worsen from baseline).
- Symptoms and/or the clinical sequelae of a suspected interaction or an overdose of either IMP or a concomitant medication.
- Signs, symptoms or the clinical sequelae resulting from special interest conditions (e.g., IMP misuse, medication error, IMP withdrawal, etc.). Overdose per se will not be reported as an AE/SAE.
- Symptoms and/or clinical sequelae that resulted in intervention.

Events that do not meet the definition of an AE include:

- Medical or surgical procedures; the condition that leads to the procedure is an AE.
- Situations where an untoward medical occurrence did not occur (e.g., social and/or convenience admission to a hospital, hospitalization for elective surgery, hospitalization for observation in the absence of an AE).
- Anticipated day-to-day fluctuations of pre-existing disease(s) or condition(s) present or detected at the start of the study that do not worsen.

### 10.1 Assessment of Adverse Events

The Investigator is ultimately responsible for assessing and reporting all AEs as outlined in the protocol. The assessment and reporting of AEs may be delegated to a medically qualified sub-Investigator, trained on this study protocol, who is listed on the delegation of authority log. All

AEs regardless of treatment group or suspected causal relationship to the IMP will be reported as described in this protocol.

Adverse events should be volunteered by the subject or solicited from the subject using a standard statement, obtained from examination of the subject at a site visit, or from observations of clinically significant laboratory values or special examination abnormal values. If an event assessed by one of the study scales requires intervention, or if in the opinion of the Investigator, it is clinically significant, then it will be reported as an AE.

All AEs are to be assessed and recorded in a timely manner and followed to resolution or until the Investigator determines that there is not an anticipated resolution. Each AE is to be documented with reference to severity, date of occurrence, duration, treatment and outcome. Furthermore, each AE is to be classified as being serious or non-serious. In addition, the Investigator must assess whether the AE is IMP-related or not.

## 10.1.1 Time Period for Collecting Adverse Events

Adverse event monitoring and reporting will begin after the subjects sign the ICF, continue throughout the study and include EOS/ET/Follow-up. Subjects will be monitored by the study site staff for untoward effects and will be released from the study after the last procedure is completed and confirmed that the subject has no residual untoward effects from the IMP that may affect safety. Treatment-emergent AEs will be defined events observed after starting administration of INDV-2000 or placebo.

Surgical procedures, planned before enrolment of the subject in the study, are not considered AEs if the condition was known before study inclusion. In this case the medical condition should be reported in the subject's medical history.

Any clinically significant symptoms will be reported as AEs. All AEs and corresponding treatment will be recorded in the eCRFs and a summary of all the safety data will be presented in the final Clinical Study Report (CSR). Any ongoing AEs will be appropriately followed up until resolution or 14 days after EOS/ET. The study site personnel will make every effort to contact the subject for a minimum of 2 attempts after which the outcome of the AE will be considered ongoing and the subject will be noted in source as lost to follow-up.

If a subject experiences the onset of an SAE within 5 days following study completion and in the opinion of the Investigator, that SAE is associated with the study drug, it will be followed and reported as described in Section 11.2.

If an SAE occurs that is deemed related to study drug, a PK sample will be taken as soon as possible after the event is reported. If possible, an additional sample should be collected when the SAE has been resolved.

## 10.1.2 Assessment of Intensity

The term "severe" is used to describe the intensity (severity) of a specific event (as in mild, moderate, or severe); the event itself, however, may be of relatively minor medical significance (such as a severe headache). This is not the same as "serious," which is based on subject/event outcome or action criteria usually associated with events that pose a threat to a subject's life or functioning. Seriousness (not severity) serves as a guide for defining regulatory reporting obligations.

Intensity	Definition
Mild	Causes transient or mild discomfort; no limitation of usual activities; no
	medical intervention required.
Moderate	Causes mild to moderate limitation in activity; some limitation of usual
	activities; no or minimal medical intervention or therapy is required.
Severe	Causes marked limitation in activity; some assistance is usually required;
	medical intervention or therapy is required; hospitalization is probable.

For vital sign assessments and clinical laboraty abnormalities considered by the Investigator to be an Adverse Event according to Section 10.1.4, the intensitiy of adverse events will be graded in accordance with the FDA Guidance for Industry: Toxicity Grading Scale for Healthy Adult and Adolescent Volunteers Enrolled in Preventive Vaccine Clinical Trials (Section 22.6, Appendix 6).

Adverse events with changes in severity should be documented as separate events.

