## 14.4 Key End Point Analyses

#### 14.4.1 Primary Endpoint

The primary endpoint for the study is the incidence, seriousness, severity, and relationship to IMP of TEAEs in the Safety Population.

For Part I of the study, a TEAE is defined as an AE with start date/time at or after IMP dosing. For Part II of the study (a cross-over design), a Period 1 (Fasted) TEAE is defined as an AE with start date/time at or after IMP dosing in Period 1 and no later than IMP dosing in Period 2, and a Period 2 (Fed) TEAE is defined as an AE with start date/time at or after IMP dosing in Period 2 and within the period of time equal to the interval from Period 1 dosing to Period 2 dosing.

The number and percentage of subjects reporting TEAEs will be presented overall, by MedDRA system organ class (SOC) and preferred term (PT), each in descending order of frequency (then alphabetically in case of ties).

IMP-related TEAEs, treatment-emergent SAEs (TESAEs), IMP-related TESAEs, TEAEs leading to death, TEAEs leading to IMP discontinuation, and TEAEs leading to IMP interruption will be presented both overall and by SOC and PT. TEAEs will also be summarized by intensity within SOC and PT. In addition, TEAEs leading to death and IMP-related TEAEs leading to death will be summarized separately by PT.

In summaries by severity and relationship to IMP, if more than one TEAE is coded to the same PT for the same subject, the subject will be counted only once for that PT using the most severe and most related occurrence. Missing severity will be summarized as "severe" and missing relatedness will be summarized as "related."

Separate listings will be presented for TEAEs, TESAEs, TEAEs leading to IMP discontinuation and TEAEs leading to death.

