9.1.9 Adverse event

For Part I of the study, a TEAE is defined as an AE with start date/time at or after IMP dosing.

For Part II of the study (a cross-over design):

A Period 1 (Fasted) TEAE is defined as an AE with start date/time at or after IMP dosing in Period 1 and no later than IMP dosing in Period 2.

A Period 2 (Fed) TEAE is defined as an AE with start date/time at or after IMP dosing in Period 2 and within the period of time equal to the interval from Period 1 dosing to Period 2 dosing.

The number and percentage of subjects reporting TEAEs and number of TEAEs will be presented both overall and by MedDRA SOC and PT, each in descending order of frequency (then alphabetically in case of ties). Separate summaries will be done for IMP-related TEAEs, treatment-emergent SAEs (TESAEs), and IMP-related TESAEs. TEAEs will also be summarized by maximum severity and by maximum toxicity grade within SOC and PT (refer to APPENDIX 3 – Tables for Laboratory Abnormalities for events with toxicity grades determined by the protocol); i.e., if more than one TEAE is coded to the same PT for the same subject, the subject will be counted only once for that PT using the most severe event for the summary by maximum severity, and using the most toxic event for the summary by maximum toxicity.

An overall summary table of TEAEs will be provided that shows incidence and number of events for each of the following:

- Any TEAE
- IMP-related TEAE
- TESAE
- IMP-related TESAE
- Severe TEAE
- TEAE with grade 3 or higher toxicity
- TEAE with outcome of study discontinuation
- Fatal TEAE

If any component of an AE starts date/time is missing such that it cannot be determined whether or not the AE was treatment-emergent, it will be counted in summaries as treatment-emergent. In summaries by relationship to IMP and severity, missing relationship will be summarized as "related" and missing severity will be summarized as "severe."

Protocol No. INDV-2000-101

Separate listings will be presented for TEAEs, TESAEs, TEAEs with outcome of study discontinuation, fatal TEAEs, and non-TEAEs.

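### Records split at every severity change, combined with a TEAE rule based on start time alone, can count one episode several times and can class an easing earlier AE as a new or Fed TEAE

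*Protocol*

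**What the plan says.** **Recording.** Protocol 10.1.2 states that "Adverse events with changes in severity should be documented as separate events". It makes no distinction between a rise and a fall in severity. Protocol 10.1 adds that "Each AE is to be documented with reference to severity, date of occurrence, duration, treatment and outcome", so date and duration are attributes of each AE record. Under Protocol 10.1.1, "Adverse event monitoring and reporting will begin after the subjects sign the ICF", and the schedules of events place an AE assessment on Day -1. An AE can therefore already be on file and unresolved when the subject is dosed.

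**Classification.** Protocol 14.4.1 has: "For Part I of the study, a TEAE is defined as an AE with start date/time at or after IMP dosing". SAP 9.1.9 repeats it. For Part II the SAP has "A Period 2 (Fed) TEAE is defined as an AE with start date/time at or after IMP dosing in Period 2", subject to an upper time limit. Neither document requires a TEAE to be a new onset or a worsening relative to the state before that dose.

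**Counting.** SAP 9.1.9 states: "The number and percentage of subjects reporting TEAEs and number of TEAEs will be presented both overall and by MedDRA SOC and PT". SAP Section 11 shows that the event count is a SAP addition; the protocol planned subject counts only. The one de-duplication rule, "the subject will be counted only once for that PT using the most severe event", serves the maximum-severity summary, with a parallel rule for maximum toxicity grade. Nothing in either document joins the records of one episode.

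**The concern.** Splitting records at severity changes is a common convention, and so is defining a TEAE by start time. The difficulty is the combination. Once an episode is cut into pieces, a piece that starts after dosing can look like a new event even when it marks improvement. The number of TEAEs then partly measures how often severity fluctuated.

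The incidence and severity of TEAEs are the primary endpoint, and the denominators are 6 active subjects per Part I cohort and 8 subjects per Part II period. A single misclassified subject is visible in a table of that size. In Part II, SAP 3.2 and the TEAE definitions make fasted Period 1 and fed Period 2. A cross-period misassignment of this kind can therefore only add events to the fed column.

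**Working it through.** The plan gives no figure to reproduce on this point. The check applies the stated rules to illustrative records and compares the result with an episode-based rule.

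**Inputs**
- Split at any severity change: Protocol 10.1.2.
- A date of occurrence for each AE: Protocol 10.1. That the split record gets its own start time is inferred from these two sections together.
- TEAE if the record starts at or after the dose: Protocol 14.4.1, SAP 9.1.9.
- Subjects: 6 active and 2 placebo per cohort, up to 9 cohorts, 8 in Part II (Protocol 4.1 and 5.1). Placebo is pooled, so up to 2 × 9 = 18.
- Assumed for illustration: Part II doses 168 h apart.

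**Event counts.** An episode with k severity changes after dosing yields k + 1 records, all starting after the dose, hence k + 1 TEAEs. The comparison rule counts one event per continuous episode and period, and only if it is new or exceeds the maximum severity before that dose.

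| Illustrative case | Rules as written | Episode-based rule |
|---|---|---|
| A. Part I: moderate from 12 h pre-dose, mild from 3 h post-dose | 1 | 0 |
| B. Post-dose mild, moderate, mild (k = 2) | 3 | 1 |
| B2. Post-dose mild, moderate, severe, moderate, mild (k = 4) | 5 | 1 |
| C. Part II: moderate from 150 h, mild from 172 h (second dose at 168 h) | Fasted 1, Fed 1 | Fasted 1, Fed 0 |
| D. Control: mild pre-dose, moderate post-dose | 1 | 1 |

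B and B2 change only the number of events, because the subject is counted once however many records exist. A and C add a record that reflects improvement. D shows that a true worsening after dosing is kept under both rules.

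**Subject incidence in cases A and C.** The change is 1/n if the subject has no other TEAE in that column (or, for a SOC or PT line, in that row), and 0 otherwise.
- Active cohort: 1/6 = 16.7 percentage points.
- Part II period: 1/8 = 12.5 points.
- Pooled placebo, if all nine cohorts run: 1/18 = 5.6 points.

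**Does the once-per-PT rule already cover this?** It selects one severity per subject and PT in the severity and toxicity summaries. It does not reduce the number of TEAEs, and it does not remove a record that should not have been classed as treatment-emergent.

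**The case against.** The other side has several good points.

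- The new start time is an inference. Neither document says that a record opened because severity fell takes a new onset date. Completion guidelines for the case report form, which the protocol mentions but which are not available here, may settle it. This stands as a condition on the whole point; if such a convention exists, the SAP should state it.
- Other text narrows the improving case. Protocol Section 10 excludes non-worsening fluctuations of conditions present at study start, Protocol 10.1.4 restricts which laboratory and vital-sign changes are reportable, and SAP 8.6 limits post-dose examination findings to new or worse ones. None of these clearly covers a symptom first recorded after consent or during Period 1.
- The circumstances are unusual. A healthy volunteer must have an unresolved AE at dosing that eases afterwards. In Part II it must be present at the second dose, at least a week after the first. An event that began soon after the first dose would have to outlast the washout, though one arising late in the interval, as in case C, would not.
- The analysis is descriptive, escalation rests on committee review rather than the final tables, and listings of TEAEs and non-TEAEs would show the parent record. This limits the consequence but does not correct the tables.
- Splitting is useful: with a start-time rule, it is what captures a pre-dose AE that worsens after dosing (case D). Joining records on PT and adjacent dates alone could also merge distinct episodes. Both points shape the fix.

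A reader might infer that every fluctuating episode inflates the primary endpoint's incidence, or that each misclassified record adds 16.7 or 12.5 points. The documents support neither. The first confuses event counts with subject counts; the second ignores any other TEAE the subject has.

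**Conclusion.** The gap is real but narrow. Provided that split records carry their own start times:

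- a post-dose episode with k severity changes contributes k + 1 to the number of TEAEs, with no effect on subject incidence;
- an AE that began between consent and dosing, or in Period 1, and eases after the next dose is classed as a new TEAE, or as a Fed TEAE in Part II.

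The second effect should be uncommon. The 16.7 and 12.5 points are the weight of one subject with no other TEAE in the column or row. They are not estimates of bias, and the documents give no AE rates from which to estimate one. The point merits a clarification in the SAP before unblinding; it does not call the design into question.

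**What to change.** Amend SAP 9.1.9 as follows.

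1. Link each record opened solely for a severity change to its parent episode. Use a link field in the eCRF or, failing that, require the same subject, the same PT, and an end date/time of one record equal to the start date/time of the next, so that separate episodes are not merged.
2. Count a linked episode once in the number of TEAEs (at most once per period in Part II), at its maximum severity.
3. Treat a continuation record as treatment-emergent, and assign it to a period, only if its severity exceeds the maximum severity before that dose. A record opened only because severity decreased is then not a new TEAE, while a worsening after dosing still counts.
4. State the start-date convention for split records, and keep every split record in the listings.

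The cost is SAP wording, a small derivation and possibly one link field. One consequence should be accepted knowingly: an AE that had eased before dosing and then returns only to its earlier peak would not count as treatment-emergent under step 3, although the listings would still show it.

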### 10.1.3 Assessment of Causality

The Investigator or a medically qualified sub-Investigator, trained on this study protocol and listed on the delegation of authority log is responsible for determining the AE relationship to the IMP.

The following categories will be used to define the relationship of an AE to the administration of the IMP:

Not Related:	Data are available to identify a clear alternative cause for the AE other than the IMP.
Related:	The cause of the AE is related to the IMP and cannot be reasonably explained by other factors (e.g., the subject's clinical state, concomitant therapy and/or other interventions).

A "reasonable possibility" is meant to convey that there are facts/evidence or arguments to suggest a causal relationship, rather than a relationship cannot be ruled out. The Investigator will use clinical judgment to determine the relationship. Alternative causes, such as natural history of the underlying diseases, concomitant therapy, other risk factors and the temporal relationship of the event to the IMP will be considered and investigated. The Investigator will also consult the

IB in the determination of his/her assessment. For each AE/SAE the Investigator must document in the medical notes that he/she has reviewed the AE/SAE and has provided an assessment of causality.

There may be situations when an SAE has occurred, and the Investigator has minimal information to include in the initial report to Indivior or designated representative. However, it is imperative that the Investigator always make an assessment of causality for every event prior to the initial transmission of the SAE data to Indivior or designated representative. The Investigator may change his/her opinion of causality in light of follow-up information and amend the SAE data collection tool accordingly. The causality assessment is one of the criteria used when determining regulatory reporting requirements.

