2 STUDY OBJECTIVES

The objectives of the study and corresponding study endpoints are detailed in Table 1.

Table 1: Objectives and related endpoints

Objective	Endpoint(s)	Analysis
Primary		
Determine the safety and tolerability of INDV-2000 over a proposed range of doses from 1 mg	Incidence, seriousness, severity, and relationship to Investigational Medicinal Product (IMP) of treatment-emergent adverse events (TEAEs) in the Safety population	Refer to Section 9.1.9
Secondary		1
Determine the maximum tolerated single dose of INDV-2000	Clinical safety assessments: Changes from baseline in laboratory evaluations, electrocardiogram (ECG) parameters, vital signs, physical examination	Refer to Sections 9.1.12, 9.1.13, 9.1.14, 9.1.15
Characterize pharmacokinetics for single doses of INDV-2000	Part I: Single Ascending Dose (SAD) under fasted condition:Plasma INDV-2000 and M12 C_{max} , t_{max} , AUC _{0-last} , AUC _{0-inf} , AUC(t1-t2; where t1-t2 represents urine collection interval t1-t2), $t_{1/2}$; plasma INDV-2000 CL/F and V_z/F .Additional PK parameters will be estimated to support these PK endpoints	Refer to Section 7
Determine potential effects of a high-fat meal on drug absorption and exposure	Part II: Food interaction: Plasma INDV-2000 and M12 C _{max} , t _{max} , AUC _{0-last} , AUC _{0-inf} , t _{1/2} ; plasma INDV-2000 CL/F and V _z /F.	Refer to Section 7

Protocol No. INDV-2000-101

Version Final 1.0 | 2021/03/30

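### Protocol 10.1.3: the two causality categories are not exhaustive, so IMP-related TEAE incidence depends on where the assessor places events that meet neither definition

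*Protocol*

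**What the plan says.** Protocol 10.1.3 introduces its scale with "The following categories will be used to define the relationship of an AE to the administration of the IMP" and then lists two entries only:

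- The first, *Not Related*, has as its condition "Data are available to identify a clear alternative cause for the AE other than the IMP".
- The second, *Related*, has as its condition "The cause of the AE is related to the IMP and cannot be reasonably explained by other factors", with the subject's clinical state, concomitant therapy and other interventions as examples of such factors.

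The next paragraph explains a term that appears in neither entry: "A 'reasonable possibility' is meant to convey that there are facts/evidence or arguments to suggest a causal relationship, rather than a relationship cannot be ruled" (the sentence ends with the word *out*). It continues "The Investigator will use clinical judgment to determine the relationship", names what to weigh, and requires a documented causality assessment for each AE and SAE. There is no intermediate category and no default for an event that satisfies neither entry.

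Relatedness is part of the primary endpoint in both documents. Protocol 14.4.1: "The primary endpoint for the study is the incidence, seriousness, severity, and relationship to IMP of TEAEs in the Safety Population". SAP Table 1: "Incidence, seriousness, severity, and relationship to Investigational Medicinal Product (IMP) of treatment-emergent adverse events (TEAEs) in the Safety population". SAP 9.1.9 tabulates IMP-related TEAEs and IMP-related TESAEs separately. The one default concerns blanks: Protocol 14.4.1 counts missing relatedness as related, and SAP 9.1.9 likewise says "missing relationship will be summarized as 'related". The SAP gives no definition of relatedness of its own, and its table of changes to the protocol-specified analyses (SAP 11) does not alter the categories.

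**The concern.** With two categories, one should be the negation of the other. Here each has its own demanding condition: one asks for positive identification of another cause, the other for attribution to the IMP plus the absence of any reasonable rival explanation. Events between the two conditions have no assigned place. The explanatory paragraph makes matters worse, because it describes a third threshold, weaker than the printed *Related* condition. Two investigators, one following the table and one following the paragraph, could code the same event differently, and each could defend the choice from the text.

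The stake is the count of IMP-related TEAEs by dose level, read from six active subjects per cohort. The same call is used outside the tables. Under Protocol 11.2.2 a SUSAR must be an SAE related to the IMP. Under Protocol 10.1.1 a related SAE prompts an extra PK sample, and association with study drug decides whether an SAE starting within 5 days after study completion is followed and reported.

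**Working it through.** The plan states no figure for related events and no power calculation (Protocol 14.2), so there is nothing of that kind to reproduce. The check has two parts.

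**1. Do the definitions cover all cases?** Take three yes/no facts about an AE: a clear alternative cause is identified from data (C); other factors reasonably explain it (R); there is evidence that the IMP is the cause (I). A clear alternative is also a reasonable one, so C without R is excluded, which leaves 6 of the 8 combinations. *Not Related* holds when C is true. *Related* holds when I is true and R is false.

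| Clear alternative (C) | Reasonable alternative (R) | Evidence for IMP (I) | Category met |
|---|---|---|---|
| no | no | no | neither |
| no | no | yes | Related |
| no | yes | no | neither |
| no | yes | yes | neither |
| yes | yes | no | Not Related |
| yes | yes | yes | Not Related |

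Two combinations meet *Not Related*, one meets *Related* and three meet neither. No combination meets both. The uncovered cases are a reasonable but not clear alternative (with or without evidence for the IMP) and no alternative with no evidence for the IMP.

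**Does another rule close the gap?** The missing-as-related rule acts on a blank. Because an assessment must be documented for every AE and SAE, these events will carry a value, and the rule does not reach them.

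**2. How far can one subject move the result?** Inputs from Protocol 5.1: 6 active and 2 placebo subjects per cohort, up to 9 cohorts, up to 8 subjects in Part II. Check on enrolment: 9 × 8 = 72 and 72 + 8 = 80, which match the stated totals. Placebo is pooled (Protocol 14.1, SAP 9.1): 9 × 2 = 18.

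For g subjects whose only candidate event is in the gap, among n subjects, related incidence changes by g/n:

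- active cohort, n = 6: 1/6 = 16.7 points; 2/6 = 33.3; 3/6 = 50.0
- Part II period, n = 8: 1/8 = 12.5 points
- pooled placebo, n = 18: 1/18 = 5.6 points. If only the five cohorts with stated doses ran, n = 5 × 2 = 10 and 1/10 = 10.0 points.

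The documents give no expected number of such subjects, so g is an assumption throughout.

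**The case against.** The strongest reply is that Protocol 10.1.3 is not meant to be applied as formal logic. It calls for clinical judgment, lists what to consider, and requires a recorded answer. Every AE therefore gets one of two values, and any binary causality scale leaves some dependence on the assessor. This stands as far as it goes: the endpoint can be computed, and a reader who infers that it cannot is going too far. But judgment supplies an answer without a rule for choosing when neither definition fits, and that part of the assessor dependence can be avoided.

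A reader might also infer that drug-related incidence is likely understated, because the strict *Related* wording pushes doubtful events out. The documents do not support a direction. *Not Related* is just as strict, so an investigator with no clear alternative cause is equally barred from it. The visible tabulation rules lean the other way: missing counts as related, and Protocol 14.4.1 takes the most related occurrence within a preferred term.

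Two further readings are too broad. An alternative that is merely possible does not put an event in the gap: if it does not reasonably explain the AE, *Related* can still apply. Nor can it be said that common Phase I complaints such as headache generally meet neither definition, since that depends on the facts of each case and the documents give no AE profile.

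The effect on inference is limited. All TEAEs are tabulated by active cohort and for pooled placebo, which allows a comparison that does not use investigator causality. Part I assessment is blinded, which limits bias between arms, although Part II is open and blinding does not make the coding reproducible. Finally, Protocol 16 promises CRF completion guidelines that are not among the documents. They may help, but they would have to supplement definitions that are incomplete as printed.

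**Conclusion.** The point holds as a defect in a stated rule. The categories leave three of six coherent combinations unassigned, and nothing else in the protocol or SAP assigns them. The consequence is that IMP-related TEAE and TESAE counts, and the relatedness call used for SUSAR classification, depend on the assessor in an unknown number of events.

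The per-subject figures in the working are sensitivities, not estimates of an effect. They assume that the reclassified subject has no other related TEAE and that groups are fully enrolled; the 5.6-point figure also needs all 9 cohorts. With six active subjects per dose, one or two such subjects could change how the dose pattern of related events looks, but the documents do not say whether that will happen. Relationship is one of four attributes in the primary endpoint; overall TEAE incidence, seriousness and severity do not pass through this definition.

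**What to change.** Reword the two entries in Protocol 10.1.3 so that one negates the other and both use the standard the section already explains:

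- *Related*: there is a reasonable possibility, meaning positive facts, evidence or arguments for causation, that the IMP caused the AE.
- *Not Related*: there is no such reasonable possibility.

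Of the three uncovered combinations, the one with evidence for the IMP would then normally be *Related*, and the two without it *Not Related*. The reported related rate could therefore move either way. The eCRF completion guidelines should carry the same wording and say how to code an event that has both a clear alternative cause and some evidence for the IMP. That event is *Not Related* today and would need a judgment under the new text. SAP 9.1.9 can stay as it is, including the rule for blanks.

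The cost is a short protocol amendment, which under Protocol 17 needs IRB approval before use, plus an update to the guidelines. No new data are needed. If cohorts have already been dosed, which the documents do not state, the CSR should note which definition applied to each cohort, since placebo subjects are pooled across cohorts.
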